6.5.10 Nasal epithelial brushings

Volunteers will undergo nasal brushings (either with Cyto-Soft Cytology Brushes or Rhinoprobes) on each side of the nose. This is a simple procedure and takes less than 5 minutes.

Materials

- Disposable non-latex gloves
- Tissues

- 5% lidocaine hydrochloride spray
- Cytology brush cutters, cleaned thoroughly with DNAZap™ solution before the procedure
- DNAZap™ (Applied Biosystems, Cat# AM9890)
- Sterile Cytosoft cytology brushes (Cyto-Soft Cytology Brush CYB-1. Cardinal Health #S7766-1A)
- Rhinoprobe curettes (Arlington Scientific, USA, curette 100 SY-96-0905)
- Nasal Epithelial Cell Collection Tubes with Media (RLT buffer +2-Mercaptoethanol (β -ME) Qiagen, West Sussex, UK)

Procedure

1. Explain procedure to patient.
2. Sit patient comfortably in a chair facing forward, with head tilted slightly back.
3. Apply local anaesthetic (5% lidocaine hydrochloride spray, 2-3 sprays per nostril) to both nostrils. Allow 2 minutes for onset of anaesthesia. (Procedure may be performed with or without local anaesthetic, according to participant preference, based on pilot studies currently in progress).
4. Give the participant a tissue for eye tearing or nose running.
5. If using Cytosoft cytology brushes: insert the cytology brush through the nasal vestibule medially along the floor of the nasal cavity and the septum, to the depth of the inferior turbinate.
6. Roll and move the brush laterally, under the inferior turbinate, to the anterolateral inferior turbinate. Rotate while moving the brush in and out, applying some pressure to the walls of the turbinate. Brush for 4 seconds.
7. Roll the brush away from the turbinate and remove from the nose.
8. Place the brush into a culture tube containing collection medium.
9. Gently agitate the brush in the culture medium for 4 seconds.
10. Cut the brush off at its handle so that it fits well in the tube.
11. Repeat if indicated.
12. If using Rhinoprobes: gently scrape the inferior turbinate twice, from posterior to anterior, remove Rhinoprobe from nose, insert cupped end into culture medium and agitate gently for 4 seconds.
13. Cap the tube and freeze at -80°C .

14. Check patient and offer further tissues if required.

6.5.11 Nasal biopsy

Biopsy of the mucosa of the inferior turbinates of the nose may be safely performed under local anaesthetic and sterile conditions with only minimal discomfort and inconvenience to the volunteer. Biopsy allows the capture of mucosal tissue for analysis. Nasal biopsy may be associated with slight bleeding and mild discomfort.

Materials

- Sterile dressing pack.
- Cotton wool balls.
- 1x Merocel (1cm x 1cm x 0.5 cm) (neurosurgical packing).
- 1x Lidocaine hydrochloride 5% + Phenylephrine hydrochloride 0.5% topical solution 2.5mls with nasal spray applicator.
- 1ml 1:1000 adrenaline.
- 2.5ml individual ampule of 10% cocaine hydrochloride.
- 1 x Thuddicum nasal speculum.
- 1 x Crock forceps.
- 2-3 x Fokken's biopsy forceps.
- 3-4 x Silver Nitrate sticks.
- 2 x 1ml syringe and needle.
- Direct (forehead-mounted) or indirect (shoulder lamp and forehead mirror) light source.
- Appropriate reagents for immediate storage/fixing of biopsy tissue.

Procedure

1. Examiner and patient to be sitting upright, leaning slightly forward, immediately opposite each other such that the examiner can easily touch the back of the patient's head. Examiner visualises nasal mucosa bilaterally, with attention to inferior turbinates, using Thuddicum's speculum under direct/indirect light.
2. Lidocaine + Phenylephrine spray applied; 3-4 sprays to each side of the nose.

3. Two minutes later, the examiner inspects decongested nasal mucosa and chooses an appropriate side for biopsy.
4. 2-3 small pieces of cotton wool (approximately 2 x 2 cm) are soaked in 2.5ml 10% cocaine hydrochloride in a sterile tray. Soaked pieces are individually placed into the appropriate side of the nose, alongside the inferior turbinate, using sterile Crock forceps.
5. Ten minutes later, the patient is asked to check whether they have an abnormal/numb sensation in their upper front teeth. If so, cotton wool can be removed; if not, check position of the cotton wool, adjust if required, and then leave it in place for a further 5 minutes.
6. Once cotton wool is removed, check that the turbinate has been anaesthetized by prodding it lightly with the tip of Crock forceps – the patient may feel pressure/movement but should not feel pain.
7. Under direct vision, using Fokken's biopsy forceps a 2 mm bite of the exposed edge of the inferior turbinate, approximately 0.5cm back from the anterior edge, will be taken. The biopsy forceps will then be passed to an assistant who will dislodge the biopsy tissue into an appropriate sterile medium.
8. The operator immediately takes a second set of Fokken's forceps and, as before, takes another biopsy of the inferior turbinate adjacent to the previous biopsy, on the same side of the nose. The sample within the forceps is then passed to the assistant as before.
9. A final third biopsy adjacent to the previous biopsies will then be taken and processed.
10. 0.5 ml of adrenaline is then added, drop-wise, to a loose cotton wool plug (or a Merocel neurosurgical sponge) and placed into the nose adjacent to the biopsy sites.
11. After at least 10 minutes the cotton wool/Merocel sponge is removed with Crock forceps.

12. Under direct vision, the biopsy sites are cauterised using silver nitrate sticks at sites of any visible bleeding.
13. The patient is given 500-1,000mg paracetamol PO and is observed for at least 15 minutes.
14. If well, the patient may then be discharged with the following advice:
 - a. Avoid nose blowing and picking for the next 5 days.
 - b. Avoid straining, heavy lifting and contact sports for the next 5 days.
 - c. Avoid alcohol for the next 24 hours.
 - d. If bleeding occurs, pinch the cartilaginous area of the nose firmly for 10 minutes. If bleeding continues, repeat up to 3 times. If bleeding persists the patient should attend their local Accident & Emergency department.
 - e. Take paracetamol 500-1000mg 6-8 hourly for the next 24 hours; continue after this if pain or discomfort persists.

Patient will be given a 24 hour contact telephone number for advice.

6.5.12 Venepuncture

Blood will be drawn from an antecubital vein using a 19 gauge butterfly (or similar) sterile cannula. Participants may experience some minor discomfort on skin puncture during insertion of the cannula. Blood samples will be taken with the volunteer sitting down. If volunteers experience faintness or frank vaso-vagal syncope due to venepuncture, they will be assisted to lie flat and blood pressure and vital signs will be monitored until symptoms resolve. Oxygen and intravenous fluids will be available in the exceptionally unlikely event that they are required. In 6 months we will not take more than 500 ml of blood as suggested by the National blood service³².

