The current trial involves a 12-month, randomised, placebo-controlled study, with a further 12-24 months open treatment and/or assessment following unblinding at 12 months. The allergen-induced early nasal response and early and late cutaneous responses, plus local and systemic allergic immunologic parameters, will be measured at baseline, before commencement of AIT. In order to assess a time-course of action, further measurements will take place at around 4, 8 and 12 weeks, at around 5 months (peak season), 6 months and 12 months (post season) of treatment. The results will build on our understanding of allergen tolerance and have the potential to identify novel targets for pharmacotherapy in the treatment of allergic disease. They may also inform novel approaches for allergen immunotherapy. A single-centre design will reduce variability and allow for detailed assessments including response to nasal allergen challenge with sampling of nasal fluid, nasal biopsy and nasal mucosal brushing, and measurement of early and late-phase skin responses. We will include 20 healthy, non-atopic participants to serve as a control group for novel biomarkers in blood samples, nasal brushings and nasal biopsies. ALK Abello (Horsholm, Denmark) will supply Grazax® tablets and matched placebo tablets.

5. Study Objectives

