6.5.14 Visits

Atopic Participants:

Scheduled Visits (screening, randomisation and blinded treatment phase):

Where possible, all study visits should occur within the time limits specified below:

Screening Visit – Visit -1, from December 2013 to April 2014.

Visit – 0a, after screening and before Visit 0b.

Visit – 0b, from January 2014 to April 2014.

Visit – 1, after Visit – 0b.

Visit – 2, from February to May 2014.

Visit – 3, from March to May 2014.

Visit – 4, from April to June 2014.

Visit – 5, from May to August 2014.

Visit – 6, from July to October, 2014

Visit – 7, from January to April 2015.

Unblinded treatment phase

Visit- 8, January-March 2016

Visit- 9, January-March 2017

Unscheduled visits:

Unscheduled visits may be performed in the event that participants experience a disease exacerbation requiring treatment or because the participant prematurely terminates from the study (see section 6.3.3).

Visit -1:**Screening visit:**

Volunteers will attend the allergy unit at the Royal Brompton Hospital for approximately 2 hours. During this visit the following will be undertaken:

- Written informed consent before any study procedures are performed.
- Demographic data (sex, date of birth, ethnic origin, medical history).
- Allergic history - record of allergic symptoms and allergic medication taken by the subject during at least the last two years.
- Physical examination and observations (weight, height, blood pressure, heart rate, peak expiratory flow rate, peak nasal inspiratory flow and spirometry).
- Participants will mark a retrospective Global evaluation (GE) visual analogue scale (VAS) (scale 0-100 mm; **Appendix 1**) and complete a retrospective GE chart (**Appendix 2**) documenting the overall severity of their hay fever symptoms during the previous pollen season.
- Participants will complete a Mini Juniper Rhinitis Quality of Life Questionnaire (mRQLQ) (**Appendix 3**) and Global evaluation scores (**Appendix 4 and 5**) corresponding to current rhinitis symptoms and medications.
- Skin prick test - standard allergen test panel as described previously.
- Blood sampling of up to 20 ml for total IgE, specific IgE to Timothy grass pollen and total blood count will be taken.
- Nasal challenge with 5,000 BU/ml Timothy grass pollen extract with TNSS recorded after 5 minutes (**Appendix 6**).
- Recording of concomitant medication.
- Evaluation of inclusion and exclusion criteria.

Visit 0a:

1st Baseline Visit:

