Volunteers meeting the inclusion and exclusion criteria will be randomised into the two arms and will come in for 60 minutes for blood sampling (120 ml), nasal lavage (wash), nasal brushings and nasal fluid collections.

Table 1: Visit 0a

Time (hr:min)		Procedure
00:00	Arrival	
00:05	Blood sampling	120ml peripheral blood
00:15	Pre-lavage	Secretion collection
00:20	Pre-lavage	Nasal brushings
00:25	Nasal-lavage	
00:55	Post-lavage	Secretion collection

Visit 0b:**2nd Baseline Visit:**

On the 2nd baseline visit participants will attend the allergy unit for a period of 2 hours in the morning and 1 hour in the evening (overall 3 hours). During this visit the following will be undertaken (see also **Table 2**):

- A period of 15 minutes acclimatization to hospital environment and relative inactivity.
- Participants will receive a nasal wash (lavage).
- Duplicate intradermal injections of 1.0 BU timothy grass allergen into the extensor surface of their right and left forearm, and a saline control injection also on the right arm will be performed. The EPR will be recorded at 15 minutes after injection; the LPR will be measured at 8 hours after injection.
- The participants will receive a nasal allergen challenge with 5,000 BU/ml Timothy grass pollen extract. The EPR after the nasal challenge will be recorded

via the TNSS score (**Appendix 6**) and VAS score (**Appendix 7**) before challenge and after 5, 15, 30 and 60 minutes.

- Peak nasal inspiratory flow (PNIF) will be assessed shortly before collecting the nasal fluid before the nasal challenge and after 5, 15, 30 and 60 minutes after the nasal challenge.
- Peak expiratory flow (Peak Flow) will be assessed before nasal allergen challenge and 60 minutes after nasal allergen challenge.
- Nasal fluid will be collected by inserting a single foam sponge into each nostril and will be left in place for 2 minutes before removal. Secretions will be collected before challenge, at 5, 15, 30 and 60 minutes after nasal challenge and after 8 hours.
- The volunteers are allowed to leave the hospital (e.g. for work) and will return in the evening (after 8 hours) to allow reading of the skin LPR. Additionally, volunteers will undergo nasal brushings on both sides and a nasal biopsy. After the biopsy, volunteers will be observed for a further 30 minutes to ensure there is no nasal bleeding, and then allowed home.
- Food and non-caffeine-containing beverages (at room temperature) will be provided to all participants.

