Table 2: Time line procedures at Visit 0b

Time (hr:min)	*Participants will be allowed to leave and return at 8hours	Procedure
00:00	Arrival	
00:15	Pre Lavage	Secretion collection
00:20	Nasal Lavage	Nasal lavage with 240 ml SinuRinse solution
00:25	Intradermal test	1BU intradermal inject to left and right forearm + saline injection
00:40	Intradermal test	EPR recorded at 15 minutes
00:50	Pre-Challenge	TNSS + VAS, PNIF, Secretion collection

00:55	Nasal Challenge	5,000 BU/ml Timothy grass pollen allergen
01:00	Early Nasal response	TNSS + VAS; PNIF; Secretion collection
01:10	Early Nasal response	TNSS + VAS; PNIF; Secretion collection
01:25	Early Nasal response	TNSS + VAS; PNIF; Secretion collection
01:55*	Early Nasal response	TNSS + VAS; PNIF; PeakFlow; Secretion collection
08:25*	Intradermal test	LPR
08:30		Secretion collection Nasal brushings Nasal biopsy

TNSS; total nasal symptom score

VAS; visual analogue scale

EPR; Early phase response

LPR; Late phase response

BU; Bioequivalent Unit

PNIF; Peak nasal inspiratory flow

Visit 1:

Initiation of treatment will take place after Visit 0 including an inspection of the nasal biopsy site. The patients will be required to remain for 60 minutes in the hospital after intake of the first AIT/Placebo.

Visit 2, 3 and 4:

After around 4, 8 and 12 weeks of treatment starting the tablets (AIT/placebo), participants will return during the morning for around 60 minutes to have a 120 ml blood sample taken. Furthermore the volunteers will fill out questionnaires and undergo nasal fluid collection and brushings. (see also **Table 3**)

Table 3: Time line procedures at Visit 2, 3 and 4

Time (Hr:min)		Procedure
00:00	Arrival	
00:05	Blood	Blood sample (120ml)
00:10	Questionnaires	mRQLQ, SMS, GE VAS
00:15	Pre-lavage	Secretion collection
00:20	Pre-lavage	Nasal brushings

00:25	Nasal-lavage	
00:55	Post-lavage	Secretion collection

GE VAS; Global Evaluation visual analogue scale

mRQLQ; miniRhinoconjunctivitis Quality of Life Questionnaire

SMS; Symptom Medication Score

At the start of May 2014, patients will receive the rescue medications (section 6.4.8.1) and will be asked to fill out the Global Evaluation (GE) VAS (**Appendix 4**), Symptom Medication Score (SMS) (**Appendix 5**) and mini-Rhinitis Quality of Life Questionnaire (mRQLQ) (**Appendix 3**) weekly until the end of July.

Visit 5:

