Around 5 months after begin of AIT/placebo and during the pollen season participants will come to the hospital for 1.5 hours. During this visit the following will be undertaken (see also **Table 4**):

- A period of 15 minutes acclimatization to hospital environment and relative inactivity.
- Participants will mark questionnaires (**Appendix 3-5**) corresponding to symptoms and rescue medication use during the current pollen season.
- Furthermore the volunteers will undergo the same procedures as in Visit 0b, plus questionnaires and with the exception of the intradermal skin test and nasal challenge.

Table 4: Time line procedures at Visit 5

Time (hr:min)		Procedure
00:00	Arrival	
00:05	Blood	Blood sample (200ml)
00:15	Pre-lavage	GE VAS; mRQLQ; SMS, secretion collection
00:20	Pre-lavage	Nasal brushing
00:25	Nasal-lavage	
00:55	Post-lavage	Secretion collection

		Nasal biopsy
--	--	--------------

GE VAS; Global Evaluation visual analogue scale

mRQLQ; mini Rhinitis Quality of Life Questionnaires

SMS; symptom medication score

Visit 6:

After 6 months of treatment and shortly after the pollen season patients will mark a retrospective GE VAS (scale 0-100 mm; **Appendix 1**), the mRQLQ (**Appendix 3**) and complete a retrospective GE chart (**Appendix 2**) documenting the overall severity of their hay fever symptoms during the previous pollen season. Also a nasal allergen challenge with 5.000 BU/ml Timothy grass pollen allergen will be undertaken. We will record the Peak Flow as well as the response to challenge for one hour at 5, 15, 30 and 60 min with TNSS + VAS and PNIF.

Time (hr:min)		Procedure
-00:15	Arrival	TNSS+VAS; GE VAS, mRQLQ, GE, PNIF; Peak Flow
00:00	Nasal Challenge	5,000 BU/ml Timothy grass pollen allergen
00:05	Early Nasal response	TNSS + VAS; PNIF
00:15	Early Nasal response	TNSS + VAS; PNIF
00:30	Early Nasal response	TNSS + VAS; PNIF
01:00	Early Nasal response	TNSS + VAS; PNIF; PeakFlow

Visit 7:

After 12 months on treatment volunteers will attend the allergy unit for a period of 2 hours in the morning and 1 hour during the evening (3 hours). During this visit the same procedures as described at Visit 0b plus a blood sample of 200 ml will be undertaken (see also **Table 2**).

Non-atopic Participants:

Scheduled Visits (screening (Visit -1), one time point assessment (Visit 1):

Screening Visit – September 1st to November 30th, 2014.

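### At the visit times and volumes in Protocol 6.5.14, an atopic participant gives 680 ml of blood in about 5 months, above the 500 ml in 6 months stated in 6.5.12

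*Protocol*

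**What the plan says.** Protocol 6.5.12 (Venepuncture) states the limit without exception: "In 6 months we will not take more than 500 ml of blood as suggested by the National blood service".

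Protocol 6.5.14 (Visits) sets the draws for atopic participants:

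- Screening: up to 20 ml.
- Visit 0a: 120 ml.
- Visits 2, 3 and 4, at around 4, 8 and 12 weeks of treatment: "participants will return during the morning for around 60 minutes to have a 120 ml blood sample taken".
- Visit 5: 200 ml (Table 4), timed as follows: "Around 5 months after begin of AIT/placebo and during the pollen season participants will come to the hospital".
- Visit 6: no blood in its table. It is timed as follows: "After 6 months of treatment and shortly after the pollen season patients will mark a retrospective GE VAS".
- Visit 7, at 12 months: 200 ml.

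The Background and Rationale gives the same later times: "at around 5 months (peak season), 6 months and 12 months (post season) of treatment". The calendar windows in 6.5.14 are introduced softly: "Where possible, all study visits should occur within the time limits specified below". SAP 7.1.1 repeats the windows for these visits but makes them mandatory.

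Protocol 6.6 (Biomarkers) keeps the same volumes on a different calendar, with the last 120 ml draw at 16 weeks and the next 200 ml draw at 7 months. Section 6.8.3.3 also has a biopsy at 7 months. SAP 7.3.2 puts the interim samples at 1, 2 and 3 months and the peak-season sample at 4 months.

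**The concern.** The limit and the schedule stand in the same protocol, and the scheduled draws from Visit 0a to Visit 5 appear to add up to well over the limit inside 6 months. If so, staff who see a participant on time must either exceed the stated volume or take less blood than the visit section specifies, and the plan does not say which gives way. The draws involved are the baseline and interim samples. These carry the time course of immunological change, which is the primary objective (5.1), and the time courses of IgG4 and of inhibition of facilitated allergen binding (FAB), which are secondary objectives 7 and 8 (5.2).

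**Working it through.** **Totals on the 6.5.14 schedule**

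- Visit 0a to Visit 5: 120 + 3 × 120 + 200 = 680 ml. Excess: 180 / 500 = 36%.
- With screening in the same 6 months: 680 + 20 = 700 ml. Excess: 200 / 500 = 40%.
- Visits 2 to 5 only: 3 × 120 + 200 = 560 ml. Excess: 60 / 500 = 12%.
- Visits 3 to 5 only: 2 × 120 + 200 = 440 ml, within the limit.

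**Does it all fall within 6 months?** Take 6 months as about 183 days and 5 months as about 152 days. The gap between Visit 0a and the first tablet is not stated. The full 680 ml falls inside 6 months if Visit 0a is at most 183 − 152 = 31 days before the first tablet. With an assumed gap of 6 to 8 weeks, Visit 0a drops out and the largest 6-month total is the 560 ml of Visits 2 to 5, still over. With Visit 5 at the SAP's 4 months, the total is 680 ml even with an 8-week gap.

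**Can the word 'around' absorb it?** Since Visits 3 to 5 fit and Visits 2 to 5 do not, the limit holds only if Visit 5 is more than about 183 days after Visit 2. With Visit 2 at day 28:

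- Visit 5 at 5 months: 152 − 28 = 124 days.
- Visit 5 at 6 months: 183 − 28 = 155 days.

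So Visit 5 would have to be about 7 months after the first tablet, later than the stated time of Visit 6.

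**Can the calendar windows absorb it?** Visit 2 may run from February to May 2014 and Visit 5 from May to August 2014. Counting 6 months as 182 to 184 days:

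- Earliest compliant Visit 5: 1 February + 182 to 184 days = 2 to 4 August.
- Latest compliant Visit 2: 31 August − 184 to 182 days = 28 February to 2 March.
- Latest first tablet that can comply, with Visit 2 at day 28: 31 January to 2 February. With Visit 2 at day 21 it is 7 to 9 February, and at day 35 it is 24 to 26 January.

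First tablets run from January to April 2014, so only the earliest starters, seen in August, could stay within the limit.

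**The 6.6 calendar.** Screening to week 16 gives 20 + 4 × 120 = 500 ml, exactly the limit. Week 4 to month 7 would give 560 ml, so it must span more than 6 months. On average month lengths it spans 213 − 28 = 185 days, 2 to 3 days more than 6 months. By calendar date the margin can vanish: for a first tablet on 1 February 2014, week 4 is 1 March and month 7 is 1 September, exactly 6 months. The slack is therefore 0 to 3 days, depending on the start date.

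**Later periods.** Visit 5 plus Visit 7 is 200 + 200 = 400 ml. The latest Visit 4 (30 June 2014) and the earliest Visit 7 (1 January 2015) are 185 days apart. No further breach arises.

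**The case against.** The strongest reply is that the protocol holds two calendars and that the limit was written for the one in 6.6, where it is about met. The root defect would then be an unreconciled timetable, with the excess volume as one consequence. This is plausible, and the fix starts there. It does not remove the conflict. The 6.6 times contradict the Study summary, the Background, section 6, the numbered visits in 6.5.14 and SAP 7.3.2. A 7-month Visit 5 would also follow the 6-month Visit 6 and, for most starters, fall after the Visit 5 window closes in August.

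A second reply is that the windows are worded as a preference and leave room to comply. That stands in part. A reader might infer that 6.5.12 and 6.5.14 can never be followed together, or that every one of the at least 44 randomised participants must exceed the limit. The documents do not support that: the conflict holds at the stated visit times, and a few early starters seen in August could comply.

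A third reply concerns weight. The limit is attributed to an outside body whose text is not available here, so how it applies to repeated research draws cannot be judged. Consent pages were removed from the reviewed text, so the volume told to participants is unknown. Both points stand. They bar any claim that 680 ml is unsafe or that participants were misinformed, but they do not reconcile the two figures.

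**Conclusion.** The inconsistency is real and should be fixed. At the 6.5.14 times and volumes, an atopic participant gives 680 ml in about 5 months against a stated 500 ml in 6 months, and up to 700 ml with screening. The 680 ml figure assumes that Visit 0a is no more than about a month before the first tablet. The breach itself does not need that assumption, because Visits 2 to 5 alone exceed the limit by 60 ml. No blood is counted at Visit 6: the Study summary and section 6 could be read as including a 6-month sample, but the Visit 6 table has none.

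A reader might infer a threat to the trial's main result. There is none. The primary endpoint is a symptom score after nasal challenge and needs no blood, and the 12-month secondary endpoints that need blood use the Visit 7 draw. What is exposed is the interim sampling and the protocol's own statement of how much blood it takes.

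**What to change.** First, use one timetable. Keep the 6.5.14 times. Correct 6.6 (16 weeks to 12 weeks, 7 months to about 5 months), the 7-month biopsy in 6.8.3.3, and the 4-month peak-season sample in SAP 7.3.2.

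Then take one of two routes:

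1. **Reduce the volumes** from Visit 0a to Visit 5 so that any rolling 6 months totals at most 500 ml including screening. That leaves 500 − 20 = 480 ml for Visits 0a to 5. The documents give no minimum volume per assay, so the sponsor should set the split by assay need, with priority to the IgG4, FAB and basophil samples. The cost is (680 − 480) / 680 = about 29% less blood for the baseline and interim assays. These serve the primary objective and secondary objectives 7 and 8 as well as exploratory work.
2. **Restate the figure in 6.5.12** as the actual 680 to 700 ml, with ethics committee agreement. The cost is a less favourable stated volume and an ethics submission. The attribution to the outside body should be checked against its source at the same time.

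Either route needs only amendment wording in the protocol and SAP. No change to the sample size or to the primary analysis follows.
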